## 3 Study Design

This is a 2 parallel cohort Phase II study. Metformin and doxycycline are the therapeutic agents. For metformin, the initial starting dose will be 500 mg orally daily for 3 days which will then be increased to 500 mg orally twice daily for 3 days, and if tolerated, further increased to 1000 mg twice daily after day 6. Subjects will maintain the maximum tolerated dose (up to 1000 mg twice daily) until the day prior to their scheduled definitive surgery. All medications should cease at least 12 hours prior to time of surgery.

For doxycycline the patients will take 100 mg by mouth every twelve hours until the day prior to their surgery. The last dose should be taken no closer than 12 hours prior to time of surgery.

**Table 1. Study Design**

Eligibility Screening	Cohort	Treatment	Week	-1	1							2							3	4	5
			Day	-1	1	2	3	4	5	6	7	8*	9	10	11	12	13	14			
	1 N=23	Doxycycline e			X	X	X	X	X	X	X	X	X	X	X	X	X	X	Surgical Resection		
		Metformin			X a	X a	X a	X b	X b	X b	X c	X c	X c	X c	X c	X c	X c				
	2 N=23	Doxycycline e			X	X	X	X	X	X	X	X	X	X	X	X	X	X			
		Metformin			X a	X a	X a	X b	X b	X b	X c	X c	X c	X c	X c	X c	X c	X c			
	Tissue d		X															X			

\* If surgery is scheduled past Day 8, patients will stay on metformin and doxycycline until the day prior to surgery.

- Metformin will be given initially with a starting dose of 500mg once a day for Days 1-3.
- Metformin will be increased to 500 mg orally twice a day for Days 4-6
- If tolerated, beginning Day 7 metformin will be increased to 1000 mg twice a day. Subjects will maintain the maximum tolerated dose (up to 1000 mg twice daily) until the day prior to their scheduled definitive surgery.
- When possible, baseline biopsy tissue is to be obtained prior to starting study medications. Two serum separator tubes of serum will be taken at the same time as the biopsy specimen (if possible), otherwise done at time of consent. If a pre-treatment sample has already been acquired and flash froze and if there is excess tissue available at resection, the second specimen will also have a piece flash frozen for metabolomic testing.
- Doxycycline will be taken once every 12 hours, with the last dose being taken at least 12 hours prior to scheduled time of definitive surgery.

**Eligibility Screening:** Trial Coordinator will screen the office charts for possible inclusion in the trial. Labs for the screening part will be available from pre-admission testing that is standard of care for initial biopsy. Participants of child bearing potential will have a pregnancy test within 14 days prior to enrollment.

**Visit 1, Day 0:** Subjects that meet the inclusion criteria after reviewing diagnosis, laboratory data and clinical chart will be approached the day of their consult or follow up with a subspecialty surgeon. The study coordinator will meet with the prospective candidates and go over the protocol, answer questions and obtain informed consent. If the subject is agreeable to the study, two 8.5 mL vials of blood will be drawn for baseline metabolomics and exosome profiling. After eligibility is confirmed, metformin and doxycycline will be dispensed. Instructions on how to take study drug will be given and times for follow up phone calls for tolerability and safety will be arranged with participants. When possible, patients will be given the option to meet with a nutritionist either in person or by phone within the first 7 days of their enrollment to fill out a 3 day dietary recall.

*Visit 2, Day of Surgery:* Patients will be approached for bottles and pill reconciliation as well as follow up of side effects and adverse events the day of final surgery. Two 8.5 mL vials of blood will be drawn for post-treatment metabolomic and exosome profiling. A specimen of the removed tumor will be taken for genomic analysis.

*Follow-up:* A follow up phone call will be performed 30 days ( $\pm 5$  days) after the last dose of metformin and doxycycline for any other side effects or adverse events. The participant's medical records will be reviewed every 3 months ( $\pm 1$  month) for 12 months to assess: overall survival, frequency of metastasis, and staging.

## 4 Study Enrollment and Withdrawal

Patients must have baseline evaluations performed prior to the first dose of study drug and must meet all inclusion and exclusion criteria. Results of all baseline evaluations will be reviewed by the Principal Investigator or treating physician prior to enrollment, to verify that all inclusion and exclusion criteria have been satisfied. In addition, the patient must be thoroughly informed about all aspects of the study, including the study visit schedule and required evaluations and all regulatory requirements for informed consent. The written informed consent must be obtained from the patient prior to screening procedures being performed. The following criteria apply to all patients enrolled onto the study unless otherwise specified.

### 4.1 Subject Inclusion Criteria

In order to be eligible for participation in this trial, the subject must:

1. Diagnosis of localized breast, uterine or cervical cancer that is either biopsy proven or suspected based on history, physical, and/or radiographic findings, and who are planned for definitive resection of the tumor without the use of neoadjuvant chemotherapy or radiation therapy at TJUH are eligible to participate.
2. Subjects must be  $\geq 18$  years of age at time of consent.
3. Subjects must be newly diagnosed or suspected to have breast, uterine (endometrial cancer with histologies including endometrioid, serous, clear cell, and carcinosarcoma) or cervical cancer.
4. Patient must be able to swallow pills.
5. Patients with serum creatinine levels less than 1.5 mg/dL.
6. Women of child bearing potential must have a negative urine or blood pregnancy test within 14 days of study enrollment.
7. Informed Consent: All subjects must be able to comprehend and sign a written informed consent document.
8. ECOG Performance status  $\leq 1$

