### 4.2 Subject Exclusion Criteria

The subject must be excluded from participating in the trial if the subject:

1. Received any prior cancer therapy for the breast, uterine, or cervical cancer that is being resected, including progesterone therapy for endometrial cancer patients.
  - a. Patients may have had prior therapy for other contra-lateral breast cancer.
2. Subjects who are pregnant or breastfeeding or may become pregnant during metformin and doxycycline administration.
3. Subjects on metformin or doxycycline for any reason during the preceding 4 weeks.
4. Diabetic subjects that are managed by taking metformin or insulin.
5. Subjects who have received iodinated contrast dye must wait 12 hours prior to starting Metformin. If a CT scan with contrast is scheduled after screening and consent, the

metformin cannot be taken until after the CT with contrast has been completed and they have waited 12 hours.

6. Patients with serum creatinine level greater than 1.5 mg/dL.
7. Patients with history of lactic or any other metabolic acidosis.
8. Patients with history of congestive heart failure stage III or greater.
9. Patients scheduled for definitive cancer surgical resection less than 7 days from beginning of study drug administration or greater than 5 weeks from beginning study drug administration.
10. Patients with history of hepatic dysfunction or hepatic disease and abnormal liver function tests defined as AST, ALT, Alk Phos, and or total bilirubin greater than 2.5 times the upper limit of normal.
  - a. Patients who have a history of hepatic dysfunction or hepatic disease and normal liver function tests will be eligible to participate.
11. Patients with a current history (in the past 30 days) of heavy drinking which is defined in accordance with CDC definition as more than 8 drinks per week for women and more than 15 drinks per week for men. A standard drink contains .6 ounces of pure alcohol. Generally, this amount of pure alcohol is found in 12-ounces of beer, 8-ounces of malt liquor, 5-ounces of wine, 1.5-ounces or a "shot" of 80-proof distilled spirits or liquor (e.g., gin, rum, vodka, or whiskey). While on study, patients should limit their alcohol consumption to no more than 8 drinks per week for women and no more than 15 drinks per week for men. Patients who feel they cannot comply with this recommendation are not eligible. Prior allergic reaction to metformin, doxycycline, or any other tetracycline antibiotic in the past.

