### **5.2 Study Product Description**

#### Metformin:

Metformin is a biguanide drug currently approved for the treatment of type 2 diabetes mellitus by the FDA. It is currently being investigated in multiple cancer treatment trials.

Metformin is the therapeutic agent in the protocol. The initial starting dose will be 500mg orally daily for 3 days which then will be increased to 500 mg twice daily and, if tolerated, further increased to 1000mg twice daily after day 6. Patients will maintain 1000 mg twice a day dosing until the day prior to their scheduled definitive surgery. This dose schedule has been shown to be well tolerated and was able to promote cellular changes consistent with beneficial anti-cancer effects in breast cancer patients (32).

The treatments to be used in this trial are outlined below in Table 2. Trial treatment should begin within 5 days of eligibility confirmation.

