C. Study treatment follow-up phone calls will occur on days 3 ±2 days and 5 (± 2 days) of dose escalation to evaluate tolerability, document AEs, and concomitant medications. If patient remains on study drugs for >7 days, study treatment follow-up phone calls will occur a minimum of once a week until surgery to evaluate tolerability, AEs, and con meds. Last doses of Metformin and Doxycycline pills should not be taken up to 12 hours before scheduled surgery time.

D. Patient must receive a minimum of 7 days of metformin and doxycycline before having definitive cancer surgery. Patients will stay on metformin and doxycycline until the day prior to surgery (up to the maximum of 5 weeks).

E. End of treatment visit may occur within 21 days ±7 days of stopping study drug.

F. Correlative study blood to be collected the morning of surgical resection.

- G. Follow up phone call will be performed 30 days ( $\pm$  5 days) after last dose of study medication for any other side effects or toxicity. Subject medical records will be reviewed every 3 months ( $\pm$  1 month) for 12 months.
- H. Urine or blood pregnancy test must be done within 14 days prior to enrollment on study for all women of childbearing potential.
- I. Physical examinations should include vital signs, weight and blood pressure
- J. Screening physical examination should include height.
- K. Concomitant medication reconciliation, and Toxicity and Adverse Event assessments should be done at every patient contact to fully capture any potential dose limiting toxicities or AEs that affect the patient's ability, willingness, and eligibility to continue taking study medications.
- L. Operative reports should be included with pathology reports in source documents when applicable.
- M. This optional assessment should be performed by a registered dietician. When applicable, the RD will meet with the patient within seven days of enrollment and record the patient's last 3 days of caloric intake and estimate their caloric intake versus their caloric needs per the Harris Benedict Equation.
- N. Tumor tissue should be flash frozen as quickly as possible after resection.
- O. Baseline tissue specimen will be obtained for comparative analysis when available.

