## 6.1 Screening Assessment

Before initiating any screening activities, the scope of the study will be explained to each patient during informed consent. Patients should be advised of any known risks inherent in the planned procedures, any alternative treatment options, their right to withdraw from the study at any time for any reason, and their right to privacy. After this explanation, patients should be asked to sign and date a Notice of Privacy Practice research authorization/HIPAA form and an IRB-approved statement of informed consent that meets the requirements of the Code of Federal Regulations (Federal Register Vol. 46, No. 17, January 27, 1981, part 50). During the screening period, subject eligibility will be determined according to the inclusion and exclusion criteria (Section 4.1,4.2). The following assessments will be performed during this time:

- Obtain informed consent and research authorization
- Inclusion/Exclusion Criteria
- Record demographics (including age) and medical history
  
- Physical exam
- Urine or Blood Pregnancy test (within 14 days for women of child bearing potential)
- Discuss and record concomitant medications
- ECOG performance status, vital signs [body temperature, blood pressure, pulse, respiratory rate, weight, height]
- Obtain histologic or (if appropriate) radiologic confirmation of disease
- Confirm eligibility according to the inclusion/exclusion criteria
- Laboratory tests (within 28 days of enrollment):
  - Hematology (CBC with diff)
  - Blood Chemistry
    - Creatinine, AST, AT, ALK Phos T Bili > 2.5 x ULN (all are SOC)
- If possible, baseline caloric intake assessment using a dietary log mediated by a nutritionist. This will take place at the patient's baseline assessment if possible and may be done via a phone interview.
  - If caloric intake is completed, a calculation of the patient's estimated caloric needs via the Harris-Benedict Equation will be performed.

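### Minor safety improvement: the only pregnancy test is timed from enrollment, so its age when home dosing starts can reach 19 days within the written windows and has no fixed limit if the start slips

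*Combined protocol and SAP*

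**What the plan says.** The 14-day window appears in four places in the combined protocol and SAP.

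- Section 4.1, inclusion criterion 6: "Women of child bearing potential must have a negative urine or blood pregnancy test within 14 days of study enrollment".
- Section 3, the eligibility screening paragraph under Table 1: "Participants of child bearing potential will have a pregnancy test within 14 days prior to enrollment".
- Section 6, study calendar footnote H: "Urine or blood pregnancy test must be done within 14 days prior to enrollment on study for all women of childbearing potential".
- Section 6.1, the screening checklist: "Urine or Blood Pregnancy test (within 14 days for women of child bearing potential". No reference date is given here.

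The calendar marks the test in the screening column only. No repeat is described at dispensing, on Day 1, during dosing or at surgery.

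On the way to first dose, Section 3 (Visit 1) says: "After eligibility is confirmed, metformin and doxycycline will be dispensed". Section 5.2 adds: "Trial treatment should begin within 5 days of eligibility confirmation", and calendar footnote A repeats this. Section 6.2 defines Week 1 Day 1 as the date the patient begins both drugs and requires no clinic visit for it. The follow-up calls are counted from the start of medication.

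Three provisions link eligibility to drug exposure. Section 4 says: "Patients must have baseline evaluations performed prior to the first dose of study drug and must meet all inclusion and exclusion criteria". Section 7.1.2 requires eligibility to be confirmed before study medication starts. Exclusion 2 in Section 4.2 bars: "Subjects who are pregnant or breastfeeding or may become pregnant during metformin and doxycycline administration".

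**The concern.** The test is there to prevent exposure of a pregnancy to metformin and doxycycline, and exclusion 2 is worded around the period of administration. The event that matters is therefore the first dose, but the window is counted back from enrollment. Between enrollment and first dose the patient holds the drug at home, the start date is a target, and no scheduled step checks how old the test has become. An optional dietician contact may fall in this interval, but it has a different purpose.

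At stake is a pregnancy that becomes detectable after the test and before the first dose, and so is missed before exposure to both drugs. This is a participant-safety matter only. It does not touch the sample size, the power or the signed-rank analysis of CAV1.

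**Working it through.** The plan states no figure for the age of the test at first dose, so there is none to reproduce. The check is date arithmetic.

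**Inputs**

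- Test window: 14 days before enrollment (Sections 3 and 4.1; Section 6, footnote H).
- Start target: 5 days after eligibility confirmation (Section 5.2; Section 6, footnote A).
- g: days by which eligibility confirmation precedes enrollment. The documents do not give it. Section 4 places the review of baseline results before enrollment, so g is 0 or more.
- Longest exposure: 35 days (Section 1.2, dosage rationale).

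**Oldest allowed test at first dose, start target kept**

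Age = 14 + (5 − g).

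| g (days) | Oldest test at first dose (days) | Excess over 14 (days) |
|---|---|---|
| 0 | 14 + 5 = 19 | 5 |
| 1 | 14 + 4 = 18 | 4 |
| 2 | 14 + 3 = 17 | 3 |
| 3 | 14 + 2 = 16 | 2 |
| 4 | 14 + 1 = 15 | 1 |
| 5 | 14 + 0 = 14 | 0 |

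**Start target missed**

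The 5 days are a recommendation, so the age has no upper limit. For illustration, with g = 0 and assumed overruns of 2 and 5 days, the age is 19 + 2 = 21 and 19 + 5 = 24 days. The overruns are assumptions, but the protocol foresees one cause of delay. Exclusion 5 in Section 4.2 defers metformin when a contrast CT is scheduled after screening and consent, until the scan is done and 12 hours have passed. It does not mention doxycycline.

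**Does another provision cap the age?**

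Section 4 requires the baseline evaluations to come before the first dose, and Section 7.1.2 requires eligibility to be confirmed before the first dose. Both fix an order of events. Neither sets a maximum interval.

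**With the window counted from first dose**

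- Oldest test at first dose: 14 days, whatever g is and whether or not the start slips.
- Gain with the target kept: 19 − 14 = 5 days at g = 0, falling to 14 − 14 = 0 at g = 5.
- Test taken at Visit 1, eligibility confirmed that day, target kept: 0 + 5 = 5 days at most.

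**What does not change**

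On the last day of a 35-day course the single test could be 19 + 34 = 53 days old as written. With the change it could still be 14 + 34 = 48 days old. The change concerns the start of exposure only.

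**The case against.** The strongest reply is that nothing is broken. A reader might infer that the protocol fails to keep its own 14-day limit. The documents do not support that reading: the limit runs to enrollment, three places say so, and no 14-day limit at first dose is stated anywhere. Timing screening tests from enrollment is permissible, and the screening laboratory tests use the same anchor with 28 days. This stands, and the point is therefore an improvement and not an error.

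Second, 19 days is a corner case. It needs a test on the earliest permitted day, enrollment on the day eligibility is confirmed, and a start on the last target day. Consent must come before study-specific screening, so a test done for the study would usually be recent. This also stands. However, footnote A accepts standard-of-care laboratory results from before consent, so an older result is possible.

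Third, the risk is already reduced. Exclusion 2 bars women who may become pregnant during administration, and Section 7.1.2 ties eligibility to the start of medication. These are real safeguards, although neither limits the age of the test.

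Fourth, a 14-day-old test at first dose leaves some of the same gap, and the longer untested interval is the dosing period. That is correct, and it is why the gain is called modest.

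Fifth, the missing reference date in Section 6.1 would mislead few readers, because three other places supply it. That is also correct, and no weight is put on it.

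**Conclusion.** The point holds as a minor, inexpensive safety improvement. Within the written windows, the oldest permitted test at first dose is 14 to 19 days. Beyond the 5-day target there is no cap. Counting from first dose gains 0 to 5 days when the target is kept and gives a firm 14-day limit when it is missed.

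The range rests on g lying between 0 and 5 days, which the documents do not state. The 21- and 24-day figures rest on assumed overruns. The number of women of childbearing potential is not given, so no count of affected patients can be offered.

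A reader might also infer that patients are left unprotected against exposure in pregnancy. The documents do not support that either: a negative test and exclusion 2 are both required. Only the age of the test at the start of dosing is left open.

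**What to change.** Use one wording in all four places (Section 3 eligibility screening, Section 4.1 criterion 6, Section 6 footnote H, Section 6.1): a negative pregnancy test, urine or blood, obtained no more than 14 days before the first dose of either study drug. State that the test is preferably done at Visit 1 before the drugs are dispensed. If dosing has not begun by the test date plus 14 days, repeat a urine test before Day 1. Writing that latest start date on the Patient Medication Diary, which patients already receive, would make the deadline visible at home.

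The cost is a phrase in four places, one more date for the coordinator to track beside the 28-day laboratory window, and an occasional repeat urine test. Testing at Visit 1 would make repeats rare. A deadline reached at home still depends on the patient or coordinator noticing it, so the coordinator should hold the date as well.

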### 4.2 Subject Exclusion Criteria

The subject must be excluded from participating in the trial if the subject:

1. Received any prior cancer therapy for the breast, uterine, or cervical cancer that is being resected, including progesterone therapy for endometrial cancer patients.
  - a. Patients may have had prior therapy for other contra-lateral breast cancer.
2. Subjects who are pregnant or breastfeeding or may become pregnant during metformin and doxycycline administration.
3. Subjects on metformin or doxycycline for any reason during the preceding 4 weeks.
4. Diabetic subjects that are managed by taking metformin or insulin.
5. Subjects who have received iodinated contrast dye must wait 12 hours prior to starting Metformin. If a CT scan with contrast is scheduled after screening and consent, the

metformin cannot be taken until after the CT with contrast has been completed and they have waited 12 hours.

6. Patients with serum creatinine level greater than 1.5 mg/dL.
7. Patients with history of lactic or any other metabolic acidosis.
8. Patients with history of congestive heart failure stage III or greater.
9. Patients scheduled for definitive cancer surgical resection less than 7 days from beginning of study drug administration or greater than 5 weeks from beginning study drug administration.
10. Patients with history of hepatic dysfunction or hepatic disease and abnormal liver function tests defined as AST, ALT, Alk Phos, and or total bilirubin greater than 2.5 times the upper limit of normal.
  - a. Patients who have a history of hepatic dysfunction or hepatic disease and normal liver function tests will be eligible to participate.
11. Patients with a current history (in the past 30 days) of heavy drinking which is defined in accordance with CDC definition as more than 8 drinks per week for women and more than 15 drinks per week for men. A standard drink contains .6 ounces of pure alcohol. Generally, this amount of pure alcohol is found in 12-ounces of beer, 8-ounces of malt liquor, 5-ounces of wine, 1.5-ounces or a "shot" of 80-proof distilled spirits or liquor (e.g., gin, rum, vodka, or whiskey). While on study, patients should limit their alcohol consumption to no more than 8 drinks per week for women and no more than 15 drinks per week for men. Patients who feel they cannot comply with this recommendation are not eligible. Prior allergic reaction to metformin, doxycycline, or any other tetracycline antibiotic in the past.
12. Patient is on medications that are contraindicated with metformin or doxycycline under current FDA recommendations. The following is a list of medications identified as class D (consider therapy modification) when treatment with metformin or doxycycline is considered:
  - o Class D:
    - Bismuth Subsalicylate
    - Cimetidine
    - Iodinated contrast agents
    - Somatropin

